In order to assure that the subject doesn't alter their natural behavior/instincts because of the Equivital vest the subjects will be told that the vest is intended to efficiently measure rough baseline readings to calibrate the more robust sensors that will be worn during the remaining behavioral tasks described below. Subjects will then be led into an office room that is equipped with various objects that may prompt exploring (e.g. books, stuffed animals, globe, etc.) and minimal furniture. A small video camera will be mounted on the ceiling of the room that will record the subject's activities during the 15-minute period. The camera will feed live images via a monitor to the experimenter's office. The purpose of videotaping subjects' activities is two-fold: 1) to be able to validate the physiological movement measures from the monitoring vest using "real-life" motor behavior and 2) for safety reasons, so that the experimenter can ensure that the subject is safe at all times. The combined time of instruction, sensor set up, and the 15-minute exploratory period will be 30 minutes.

Reward-related Paradigms

Monetary Incentive Delay Task (MID)^[66-68]: The MID is among the most robust methodologies in eliciting striatal activation and identifying reduced caudate activation in depression. On each trial, subjects are given a cue for potential reward (circle), loss (square), or no reward/loss (circle/ square). Horizontal lines in the cue indicate three reward/loss levels. To receive reward or avoid loss, subjects quickly press a button after seeing a target (white square). Task difficulty is adjusted to reflect each subject's skill level on the task using pre-scan reaction time

Page 12 of 30

assessment so that each subject will succeed on ~66% of trials and earns \$0-40. The MID lasts 18 minutes and will be conducted during fMRI at baseline and again without fMRI post-treatment.

Signal Detection Reinforcement Task (SDRT)^[69]: For each SDRT trial, a cartoon face (without a mouth) is displayed. A short or long mouth is shown for 100ms (pseudo-randomized and counterbalanced). Subjects identify by button press the type of mouth presented. One mouth type is associated with three times more positive feedback (monetary value) than the other. The task difficultly is similarly rigged as in the MID so that out of 300 total trials the subject will be awarded for 120. For the entire task, subjects are awarded ~\$6. Severity of depression has been shown to relate to deficiencies in developing response biases for rewarded trials on this task⁽⁸⁹⁾. The SDRT lasts 10 minutes and will be conducted both at baseline and post-treatment.

Threat-Relevant Paradigms

Backward Masking Task (BMT)^[70]: At the beginning of the run the subject will be sequentially shown two images of emotionally neutral faces. This is the target. For each of the proceeding trials the subjects will be shown an emotional face followed by another neutral face. The pairs include sad-neutral (SN), happy-neutral (HN), fear-neutral, neutral-neutral (NN; only shown at the beginning of the run), and the contrasting orders (i.e., NF). The goal is to identify if the pair of faces in each trial match the target. The images will be obtained from the NimStim Faces database⁽⁷¹⁾. The first face is shown for 26ms, followed by the neutral or "masking" face for 107ms. Each pair type is shown eight times during each of four runs in mixed-trial design. The BMT lasts 18 min. and will be conducted during fMRI at baseline and again post-treatment without fMRI. This task is expected to elicit amygdala activation according to the emotional stimuli of each trial. We believe that this task will elicit amygdala activations such that:

- Depression severity will correlate to greater activation in response to SN or NS faces.
- Anxiety severity will correlate to greater activation in response to FN or NF faces.
- The correlations between depression/anxiety severity and HN or NH faces will be observable.

Approach-Avoidance Task (AAT): This task will assess the behavioral avoidance tendencies associated with anxiety. For this tasks subjects will be shown a picture of a face (happy, angry, or neutral) framed by a blue or yellow border and instructed to pull a joystick (approach) when the border is one color and push away (avoid) when it is the other (counterbalanced). The picture zooms out and in accordingly. Mean response latency for push is subtracted from pull (e.g., angry faces pull - angry faces push) to obtain an avoidance bias score. Preliminary analyses by the PI suggest that greater trait anxiety relates to greater avoidance bias for negative stimuli. This replicates previous research in SAD^[71] and spider phobia^[72]. This task will be conducted at baseline and post-treatment behavior sessions and lasts 12 minutes.

Modified Probe Detection Task (MPDT): Attentional bias for positive and negative information will be measured using a version of the modified probe detection task [73]). Each trial consists of the identification of a cue location, brief presentation of a cue at that location (a small line oriented either horizontally or vertically), presentation of a pair of images (one representational, one non-representational), and presentation of a target, which is another line in either of two locations and is either horizontal or vertical. This target is presented until the participant responds, indicating whether the target is of the same or different orientation from the cue. Representational [73] stimuli will comprise IAPS images taken from positive, negative, or neutral valence sets. Each representational image is paired with one non-representational image, taken from a set of images of abstract art. Participants are presented with a total of 192 trials: 64 from each of positive, negative, and neutral images. The following traits are balanced across trials: representational image location, cue location, cue orientation, target location, target orientation, image duration (500 or 1000ms). The main outcome measures are the positive and negative engagement and disengagement biases [74].

Neuropsychological Assessment:

Page 13 of 30

The neuropsychological assessments will be administered by a trained examiner

Wide Range Achievement Test (WRAT-4 reading): The WRAT-4 is an individually administered test of reading designed to measure general academic competence. The main variable of interest will be the total words pronounces correctly [193].

Delis-Kaplan Executive Function System (D-KEFS) Color-Word Inhibition Test: The D-KEFS Color-Word Inhibition Test is designed to assess verbal response inhibition and attentional switching. Participants are asked to name patches of colored ink (Color Naming subtest), read color-related words (Word Reading subtest), or to name the ink that colorrelated words are written in (Inhibition subtest). The speed at which participants complete the task and the number of mistakes made during completion are recorded. The main variables of interest for this study are the total time to complete the word reading, color naming, inhibition, and inhibition/switching subtests [75].

Delis-Kaplan Executive Function System (DKEFS) Verbal Fluency: This test is meant to measure information retrieval that is under conscious cognitive control and presumably an aspect of executive functions. On each of six oneminute trials, the examinee is asked to say as many distinct words as possible that meet a certain criterion. For the first three trials, the words must begin with a particular letter, for the next two trials, the words must belong to a particular semantic category, and for the last trial, words must alternate between two semantic categories. The main variable of interest is the total number of words correctly identified for the letter subtests and the semantic category subtests [75].

Wechsler Adult Intelligence Scale (WAIS-IV) Digit Span: This sub-test of the WAIS-IV is used to assess attention and working memory and requires participants to repeat a series of numbers in forwards and backwards order (Digit Span). The accuracy of their responses is recorded. The main variables of interest are the total score forward and backward [76].

Finger Tapping Test (FTT): The FTT is a neuropsychological test that examines motor functioning, specifically, motor speed and has also been shown as a sensitive measure of testing effort [77]. The main variables of interest are the average number of taps with the index finger per 10 seconds for dominant and non-dominant hands. WAIS-IV Digit Symbol Coding [76] The Digit Symbol is a neuropsychological test of visuomotor speed and working memory. The test requires individuals to match a symbol to a number according to a key at the top of the page. The main variable of interest will be the number of symbols matched in the time limit (90 seconds).

Neuroimaging using MRI

We will conduct the MRI behavioral tasks described above simultaneously with both EEG and MRI in order to ascertain the relationship between anxious systems and neural responses during emotional, cognitive, and interoceptive processing. If there is reason to believe a subject may not be able to tolerate the MRI, the subject may be asked to complete a mock MRI scan to verify MRI tolerability. If they are unable to tolerate MRI scanning, they will be withdrawn from the study and be provided prorated reimbursement for the time spent on the study. The mock scanner simulates the look, sound and feel of a real MRI scanner. The mock scan appointment takes about 30 minutes.

Prior to scanning, each subject will complete (1) self-report assessment of sleepiness (2) review of fMRI procedures and MRI safety screen, (3) review of instructions to complete the tasks (described above), and completion of practice tasks to ensure comprehension of instructions. This pre-scan preparation is estimated to take approximately 15 minutes. Participants will be scanned in a GE Discovery MR750 3.0 Tesla scanner (GE Medical Systems) at the Laureate Institute for Brain Research. The scanner is equipped with system-standard 8- and 32channel brain coils. The multi-element brain arrays are highly sensitive MRI signal detectors offering vastly improved sensitivity for the detection of functional activation induced signal changes at high spatial and temporal resolutions, as well as anatomical MRI at very high spatial resolutions. The receivers allow for shorter readout times and reduced signal distortions and ventromedial signal dropout. During the functional neuroimaging scanning session, EEG data recordings will be collected via a state-of-the-art 8-channel MRI-compatible EEG system (Brain Products, GmbH, Germany, USA branch: Brain Vision LLC, Morrisville, NC). The customized system allows for accurate correction of MRI artifacts and high-quality EEG signals acquired simultaneously during fMRI. Each of the

Page 14 of 30

two imaging sessions (conducted pre and post treatment) will take approximately 60 to 120 minutes. Each subject will be thoroughly screened for MRI safety.

MRI preparation

MRI eligibility will be confirmed prior to entry into the scanner. The subject will be asked to remove all ferromagnetic items. The subject will be trained on all fMRI tasks and given time to practice. If the subject requires vision correction, he or she will be fitted with plastic glasses closely matching his optic prescription. A urine sample will be collected for a pregnancy test (for female participants). Earplugs will be inserted prior to entering the scanner. The audio system will be explained so the participant will know how to communicate with the scanner operator and headphones will be placed over the ears. The subject will be reminded of the importance of staying still in the scanner. To minimize motion, the participant's head will be stabilized with a specially designed pillow under the neck and wedge-shaped cushions between the sides of the head and head-holder. Padding will be arranged to maximize comfort and a pillow will be placed under the knees to provide lower back relief. The MRI operator will put the head coil in position over the participant's head, localize the head position on the scanner, and ensure that the subject can fully view the display screen at the end of the scanner gurney, where task images will be displayed, by looking in the mirror directly above their eyes. The response box will be positioned in the subject's dominant hand and the subject will test the buttons. In the subjects' non-dominant hand, the pulse oximeter is placed on one finger and the subject is provided the emergency squeeze ball. Once the subject is comfortable, the gurney will move into the magnet. The MRI technician will secure the scan room door, dim the scan room lights, and communicate with the participant through the console.

Plan of Action for Incidental Findings

Upon detection of incidental findings during MRI scanning, the researcher or medical doctor at LIBR will verbally and/or in writing communicate the discovery to the subject. The communication will guide the subject to make the discovery known to their primary-care physician and that the Laureate Institute for Brain Research will provide a digital copy of the suspect MR scans to the primary-care physician upon request once the subject provides written consent authorizing the release of these medical records. Additionally, detection and disclosure of incidental findings will be documented in a database contained on the Laureate Institute for Brain Research computer cluster.

Physiological Monitoring

Physiological noise estimation and correction will be acquired through physiological monitoring of pulse rate using a fingertip pulse oximeter throughout the MRI session. An elevated pulse rate will generate a query from the scanner operator. Pulse rates above 90 beats per minute will prompt the scanner operator to ask participant if they are okay. The pulse oximeter sensors are connected to an In Vivo physiological monitoring system. Collection of physiological data during the scan will be linked to the behavioral tasks by a pulse marker generated by the magnet console and recorded on the physiological tracings. The concurrent information on pulse rate will be used to remove physiological fluctuations from the fMRI data.

Psychophysiological Recordings:

Subjects will perform behavioral tasks (outside of the scanner) while having their psychophysiological activity recorded using the measures described below. All measures will be taken using BIOPAC instrumentation (Lehigh, Pennsylvania). BIOPAC Systems provides both hardware for collection of these measures (BioPac MP150 system) and software (AcqKnowledge software) for analyzing these measures. All of these measures are commonly used in emotional processing research and are non-invasive. The use of all of these measures concurrently allows for a more thorough understanding of sympathetic and parasympathetic nervous system influences on physiological responses to negatively and positively-valenced stimuli, interoceptive stimuli, cognitive processing and decision-making. The combined time for both sensor set up and task completion is 2.5 to 3 hours.

Galvanic Skin Conductance Level and Response: Electrodes are used to measure variations in sweat gland activity that has been shown to vary due to stress and emotional arousal. Galvanic skin conductance responses to emotional stimuli have been shown to vary with individual anxiety levels. To measure galvanic skin conductance small electrodes are placed on the skin at either the fingertips, palm of the hand, or soles of the feet with isotonic gel (0.5% saline in a neutral base). Skin conductance has long been considered as a physiological marker of emotional arousal^[78] and is often described as a non-specific measure of arousal, regardless of the valence of a stimulus^[79]. Skin conductance measures have been shown to vary not only with the arousal state of the individual, but also by the more chronic emotional state – for example, with those reporting higher levels of trait anxiety demonstrating increased skin conductance responses^[80].

Heart rate: Measures related to heart rate will be obtained from (1) pulse oximetry and (2) electrocardiogram (ECG). For pulse oximetry, BioPac systems use Nonin's PureLight® sensors to noninvasively measure blood-oxygen percentage levels via light-emitting diodes (LEDs) placed onto either the earlobe or fingertip. Light absorption differs between oxyhemoglobin and its deoxygenated hemoglobin and thus can be used to obtain the oxyhemoglobin/deoxyhemoglobin ratio and pulse rate. Heart rate has consistently been shown to increase under states of high arousal, particularly emotional arousal and anxiety. State changes in arousal and anxiety have been consistently found to relate to increased heart rate, which is considered primarily under sympathetic nervous system control^[81, 82]. For ECG, Biopac systems will again be used, along with three Ag/AgCl electrodes placed on the subject's chest (to the right or left clavicle and to the left of the belly button) in order to obtain a measure of the electrical activity of the heart. Data collected from this measure can be used to estimate heart rate variability (oscillations in the interval between consecutive heart beats) and, when combined with measures of respiration rate, respiratory sinus arrhythmia (RSA; variation in heart rate that occurs during a breathing cycle). While skin conductance and startle responses are thought to be primarily controlled by sympathetic nervous system inputs, heart rate variability and RSA are thought to result from the interaction of sympathetic and parasympathetic inputs^[83]. Individuals with a variety of mood and anxiety disorders have been reported to decrease HRV and RSA^{[81,} 84]

Respiration Rate: Respiratory effort will be measured using BIOPAC's Respiration Transducer, which measures changes in thoracic or abdominal circumference that occur as the subject breathes. This is accomplished via a belt that wraps around the abdominal or thoracic region of the body, which noninvasively measures changes in stretch of the belt with circumference change. High levels of anxiety, particularly anxiety sensitivity and/or panic disorder have been associated with increased respiratory rate in response to anxiogenic stimuli^[85]. In addition respiration rate will be used in conjunction with ECG to estimate RSA, as indicated above.

Startle Reflex Electromyogram: Electromyogram (EMG) responses will be measured from the orbicularis oculi using two electrodes filled with electrode gel and fitted with adhesive collars. One electrode will be placed directly underneath the left eye, and another one approximately 1 cm to the left below the outside corner of the left eye. The startle reflex is sensitive to habituation, sensitization, and affective context and modulation. Eye blink startle is a reflexive response and thus, no heavily influenced by intentional control or response biases that can interfere with self-report, and represents a translational tool that has been used with both humans and other animals. Startle amplitude has been consistently shown to vary with induced affective state as well as trait levels of mood and anxiety. It represents the one psychophysiological measure that may track valence rather than arousal only^[86, 87].

Facial Expressions: Advances in computer vision and machine learning over the past 15 years have led to the emergence of technology for automatic analysis of affective behavior^[88]. During this time, the Machine Perception Laboratory at UCSD (MPLab) has focused on development of systems for automatic analysis of facial behavior, including audio-visual speech recognition ^[89-91] and recognition of facial expressions ^[90-94]. The output of the face detector is scaled to 90x90 and fed directly to the facial expression analysis system. First the face image is passed

Page 16 of 30

through a bank of Gabor filters at 8 orientations and 9 scales (2-32 pixels/cycle at 0.5 octave steps). The filterbank representations are then channeled to a classifier to code the image in terms of a set of expression dimensions. Research at the MPLab has demonstrated that performing feature selection on the Gabor filters prior to classification enhances both speed and accuracy. This approach combines feature selection based on Adaboost with feature integration using support vector machine. *Automatic Facial Expression Analysis*: A video camera will record each subject during the behavioral tasks described above in order to permit coding of facial expressions. Automatic facial expression analysis will be conducted by the EMOTIENT ^[95], software developed and validated by our collaborators at the Machine Perception Laboratory at UCSD (MPLab). EMOTIENT analysis corresponds to the well-validated Facial Action Coding System (FACS ^[96, 97]), a comprehensive method to objectively code facial expressions. EMOTIENT automatically codes the intensity of 26 component facial movements referred to as action units (Aus).

Blood biomarkers:

Under the direction of the [name], biochemical assays will be performed on biological samples collected at baseline and post-treatment to quantify biomarkers linked with changes in functional improvement with therapy for anxiety and depression. Participants will be asked to have fasting blood drawn by a trained phlebotomist (conducted prior to 11am to reduce the length of fasting and increase consistency across samples drawn). This will be scheduled to occur the morning of one of the visits, or at a time convenient for the participant. Resting blood pressure and heart rate will be assessed. Extra blood samples will be obtained to examine a standard panel of metabolic and inflammatory biomarkers, including leptin, glucose, insulin, a lipid panel, soluble cellular adhesion molecules (sICAM, sVCAM), C-reactive protein, IL-6, and TNFa. Additionally, in order to lay the foundation for future studies, we also propose to collect and process a small quantity of blood (40 mL) to be banked for potential future endocrine, immune and/or genomic analyses.

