Aim2: Identify approach-avoidance behaviors and neural responses that predict the effectiveness of exposure-based behavioral therapy (EXP) for anxious subjects and behavioral activation therapy (BA) for depressed subjects.

Hypothesis 2.1: Approach-related behaviors and/or conflict arbitration behavior will help predict treatment response above and beyond avoidance-related behavior and baseline symptom severity. Specifically, we expect that difficulties with conflict arbitration will predict nonresponse of anxiety patients to EXP and that decreased reward sensitivity will predict nonresponse of depressed patients to BA.

Hypothesis 2.2: Approach-related and conflict arbitration neural circuitry will help to predict treatment response above and beyond activations within avoidance-related neural circuitry. Specifically, we expect prefrontal responsivity during conflict arbitration to predict response of anxiety patients to EXP and striatal responsivity to reward to predict response of depressed patients to BA.

Aim 3: Identify whether functional improvement with EXP or BA is associated with change in approach-avoidance behaviors.

Hypothesis 3.1: The level of change in conflict arbitration behavior will positively relate to the level of improvement in overall functioning with EXP.

Hypothesis 3.2: The level of change in reward sensitivity will positively relate to the level of improvement in overall functioning with BA.

Aim 4: Identify whether functional improvement with EXP or BA is associated with baseline metabolic and inflammatory markers, as measured via blood assays.

Hypothesis 4.1: The elevation of inflammatory biomarkers (i.e., ratio of uinolinic acid [QA] relative to kynurenic acid [KynA]) will relate to less improvement with treatment.

Aim 5: Identify whether Behavioral Activation is as or more effective for Generalized Anxiety Disorder (GAD) than exposure therapy.

Page 2 of 30

Hypothesis 5.1: Behavioral Activation will be equally effective to exposure therapy for individuals with GAD as their primary mental health diagnosis.

B. BACKGROUND AND SIGNIFICANCE

Current Anxiety and Depression Treatment Effectiveness

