Studies emerging from both primary care and psychiatric settings have shown substantial comorbidity between anxiety and depression^[21-24]. These results have been seen across various demographics including children, adolescents, and adults. When self-report rating scales for anxiety and depression are used, typically only two or three dimensions of symptoms are found in which symptoms of depression emerge distinct from symptoms of anxiety^[21-24]. When anxiety and depression are assessed at syndrome or diagnostic levels, high correlations remain. Moreover, studies of adults suggest that both disorders often share common risk factors and that similar interventions may be effective^[25]. However, there have been important neural differences identified, particular in relation to striatal circuitry and reward processing [26-30]. Thus, the current study will attempt to identify similar or unique therapy predictors for primary anxiety and primary depression (using EXP and BA, respectively). We will also include those with comorbid anxiety and depression, but will enroll them in the treatment that corresponds to the disorders/symptoms of most concern for the patient. As the comorbidity is extremely high (i.e., 88%) between generalized anxiety disorder (GAD) and depression in particular [31], this makes it difficult to determine which treatment these individuals should be provided. It has often been proposed that GAD is a form of depression with slight variance in symptoms [31]. Thus, it is possible that therapies effective in reducing depressive symptoms may also be effective for individuals with GAD. Thus, in the current study, those who meet criteria for GAD as their primarily clinical complaint, will be randomized to receive either BA or EXP. This will allow us to address Aim 5.

Approach and Avoidance in Anxiety and Depression

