Subjects will be recruited using the pre-approved LIBR screening protocol (WIRB #20101611) and from the Laureate Psychiatric Clinic and Hospital (LPCH), community mental health clinics, and the general community through clinician referral, Facebook ads, and print advertisement. Advertisement materials are included with this application.

Inclusion Criteria

- 1. Age: 18-55
- 2. All genders
- 3. All races
- 4. Eligibility as clinically significant anxiety and/or depression will be determined by:
 - a. Scoring greater than 9 on the Patient Health Questionnaire (PHQ-9) and/or greater than 7 on the Overall Anxiety Severity and Impairment Scale (OASIS)
 - b. Self-report that they are interested in obtaining treatment for anxiety or depression.
 - c. Through structured diagnostic interviews, it is determined that anxiety symptoms (generalized anxiety, panic, or social anxiety) or depressive symptoms are the primary disorder of concern. For subjects with comorbid anxiety/depression, they will be assigned to therapy for the symptoms (anxiety or depression) they report as their primary concern. Those with a PHQ-9 score >17 (moderately severe to sever range) will be asked to complete the therapy for depression, as Behavioral Activation has been shown effective for severe depression (while exposure therapy has not been shown effective in severe depression). Those who meet diagnostic criteria for GAD will be randomized to BA or EXP due to the high comorbidity and similarities with symptoms of depression.
- 5. Able to provide written, informed consent
- 6. Have sufficient proficiency in English language to understand and complete interviews, questionnaires, and all other study procedures

Exclusion Criteria:

 Has a history of unstable liver or renal insufficiency; glaucoma; significant and unstable cardiac, vascular, pulmonary, gastrointestinal, endocrine, neurologic, hematologic, rheumatologic, or metabolic disturbance; or any other condition that, in the opinion of the investigator, would make participation not be in the best interest

Page 6 of 30

(e.g., compromise the well-being) of the subject or that could prevent, limit, or confound the protocol-specified assessments.

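### Inclusion criterion 4c gives a patient with primary GAD and PHQ-9 above 17 two unranked allocations, and 4c and section F omit the limit to primary GAD

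*Protocol*

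**What the plan says.** Criterion 4c (section D, Inclusion Criteria) opens with the condition that "anxiety symptoms (generalized anxiety, panic, or social anxiety) or depressive symptoms are the primary disorder of concern". Three allocation rules follow:

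- Patients with both anxiety and depression go to the therapy for whichever they name as their main concern.
- Severity rule: "Those with a PHQ-9 score >17 (moderately severe to sever range) will be asked to complete the therapy for depression". The reason given is that BA works in severe depression, "while exposure therapy has not been shown effective in severe depression".
- GAD rule: "Those who meet diagnostic criteria for GAD will be randomized to BA or EXP", because of the high comorbidity and the overlap with depressive symptoms.

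Section F (Treatment) repeats the GAD rule as an exception to disorder-matched therapy, without mentioning the PHQ-9. The list uses blocks of 4 within gender.

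Two places are narrower about who is randomised. Section B (Anxiety and Depressive Disorder Comorbidity) says "those who meet criteria for GAD as their primarily clinical complaint, will be randomized to receive either BA or EXP". Hypothesis 5.1 reads "Behavioral Activation will be equally effective to exposure therapy for individuals with GAD as their primary mental health diagnosis".

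**The concern.** Aim 5 is the only randomised comparison in the study, so the rule for entering it should give one answer per patient. For primary GAD with PHQ-9 above 17 it gives two. Staff who follow the severity sentence place the patient in BA and keep the patient out of the randomised group. Staff who follow the GAD sentence randomise the patient, possibly to EXP. Both would be following the protocol.

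Two things are at stake. Hypothesis 5.1 would be tested in a different population depending on the reading. And some patients could receive a therapy that the same criterion says lacks evidence in severe depression. An analysis plan can define the Aim 5 set afterwards, but it cannot decide which therapy a patient gets at enrolment.

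The missing limit to primary GAD raises a related question: whether a patient whose GAD is secondary to, say, panic disorder or depression should be randomised at all.

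**Working it through.** No figure in the protocol bears on this, so the check is to run patient types through each allocation statement. Hypothesis 5.1 names a population but allocates no one, so it is used only to see who falls inside Aim 5.

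| Patient | Severity sentence, 4c | GAD sentence, 4c, and section F | Section B |
|---|---|---|---|
| Primary GAD, PHQ-9 of 17 or less | does not apply | randomised | randomised |
| Primary GAD, PHQ-9 above 17 | BA | randomised | randomised |
| Secondary GAD, PHQ-9 of 17 or less | does not apply | randomised, read literally | not randomised |
| Secondary GAD, PHQ-9 above 17 | BA | randomised, read literally | not randomised |

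**Row 1.** The comorbidity sentence in 4c, taken alone, would send a primary-GAD patient who also has depression to therapy for the reported concern. 4c does not rank that sentence against the GAD sentence either. Section B resolves this case: it gives the comorbidity itself as the reason for randomising.

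**Row 2.** Nothing resolves this case. The threshold of 17 appears only in 4c. Section B and section F repeat the GAD rule without it, and the exception in section F is to disorder-matched therapy, not to the severity rule. With equal allocation within blocks of 4 (an assumption, since the ratio is not stated), the chance of EXP is 2/4 = 1/2 under the GAD rule. Under the severity rule it is 0.

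**Can row 2 occur?** Yes. Criterion 4a sets a lower PHQ-9 bound (above 9, and/or OASIS above 7) but no upper one, and no exclusion criterion removes severe depression as such. Section B says that "the comorbidity is extremely high (i.e., 88%) between generalized anxiety disorder (GAD) and depression", so depressive symptoms are expected in this group.

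**Rows 3 and 4.** Section B and Hypothesis 5.1 require GAD to be primary; 4c and section F do not say so. Read literally, they randomise patients with secondary GAD, against the primary-concern rule in 4c and outside the population of Hypothesis 5.1. The opening of 4c suggests that the primary limit is intended, so this is a gap in wording.

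**The case against.** The strongest reply is that the text already leans one way. Sections B, D and F all randomise GAD patients and none makes a PHQ-9 exception. Section B says GAD is randomised because depression so often accompanies it, so depressed GAD patients are the very reason for the rule. Within 4c the GAD sentence comes last and is more specific. The severity sentence only says patients will be asked, and it can be read as a limit on the preference rule just before it. This stands as a description of the likelier intent. It does not close the gap, because the reason given for the severity rule applies equally to a severely depressed patient with GAD, and no reason is given for setting it aside.

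The possible harm should not be overstated. The protocol describes the band above 17 as moderately severe to severe, which is wider than the severe depression named in its caveat. Section F says the manual from which EXP is adapted reduced anxiety symptoms in GAD. Section H provides weekly symptom monitoring and referral.

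A reader might also infer that Aim 5 is biased because the BA arm collects the more severe cases. The documents do not support that. Either rule, applied consistently, leaves a valid randomised comparison and changes only its population. Bias of that kind would need BA patients placed by the severity rule to be pooled with the randomised ones, and nothing says they will be.

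Nor can the 88% be turned into a share of patients affected. Its direction and time frame are not stated, and the protocol does not say how many GAD patients score above 17.

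**Conclusion.** The point holds as an unranked pair of allocation rules in criterion 4c, together with a missing limit to primary GAD in 4c and section F. It should be fixed, because it concerns entry to the only randomised comparison and the therapy given at enrolment.

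For a patient with primary GAD and PHQ-9 above 17, the chance of EXP is 0 or 1/2 depending on which sentence is followed, assuming equal allocation. How many patients this touches cannot be worked out from the protocol. The missing word is the lesser part, since section B, Hypothesis 5.1 and the opening of 4c all point to primary GAD. The conclusion does not extend to bias in the Aim 5 estimate.

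**What to change.** In criterion 4c and section F, write *GAD as the primary disorder* and add one clause of precedence. Either choice is workable, and it is the sponsor's to make:

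- (a) Patients with PHQ-9 above 17 go to BA and are not randomised. The Aim 5 conclusion is then limited to primary GAD with PHQ-9 of 17 or less.
- (b) GAD randomisation overrides the PHQ-9 rule, with a stated reason why EXP is acceptable for these patients.

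Under (a), add that patients placed in BA by the severity rule are not counted in the randomised Aim 5 comparison.

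The cost is wording in two places. The PHQ-9 and the diagnostic interview are already part of screening (section E), and the list is stratified by gender only, so neither option changes it. Option (a) narrows the Aim 5 population by a share that the protocol does not give, so recruitment takes longer or the set is smaller. Option (b) sends some patients with PHQ-9 above 17 to EXP.
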